1.0 SUMMARY

Sponsor: Advaxis, Inc.	Name of Finished Product: ADXS11-001 MEDI4736	Type of Treatment: ADXS11-001: Lm-LLO Immunotherapy MEDI4736: MEDI4736 is a human monoclonal antibody (mAb) of the IgG1κ subclass that inhibits binding of programmed cell death-1 ligand (PD-L1) to programmed cell death-1 (PD-1) and CD8
Study Title:	Phase 1-2 Study of ADXS11-001 or MEDI4736 Alone or In Combination In Recurrent/ Metastatic Cervical or HPV+ Head & Neck Cancer	
Trial Phase	Phase I/II	
Clinical Indication	Locally advanced, or metastatic squamous or non-squamous carcinoma of the cervix or HPV+ squamous cell carcinoma of the Head and Neck	
Trial Type	Interventional	
Study Centers	Multicenter, US-only	
Route of Administration	Intravenous (IV)	
Trial Blinding	Open label, unblinded	
Number of Trial Subjects	Approximately 66 
• 6-18 in Phase 1 (Part A) portion of study• 48 in Phase 2 (Part B) portion of study	
Estimated Duration of Trial	Approximately 4 years	
Duration of Participation	Each subject will participate in the trial for up to 4 years from the time the subject signs ICF through the final contact. Treatment will continue for up to 1 year or until the subjects has either documented progression, unacceptable adverse events, withdrawn due to investigator's discretion, subject withdraws consent, pregnancy, or noncompliance with study procedures or treatments. During treatment, subjects who achieve a CR should receive at least 1 additional cycle of treatment. Subjects who stop study treatment after a CR may be eligible for an additional 1 year of study retreatment if they progress within 1 year of stopping study treatment and the study is open. After the end of treatment, each subject will be followed for adverse events for a minimum of 30 days and for serious adverse events for 90 days.	
Randomization Ratio	There is no randomization in the Part A portion of the study. The Part B portion of the study will have a 1:1:2 randomization of ADXS11-001: MEDI4736: ADXS11-001+MEDI4736, respectively	
Methodology	This is a 2 part study in subjects with either metastatic squamous or non-squamous carcinoma of the cervix or metastatic HPV+ squamous cell cancer of the head and neck (SCCHN). Part A of the study is a Phase 1 dose escalation evaluation of the combination of ADXS11-001 and MEDI4736. The Phase 1 portion of the study will utilize a “3+3” design which will dictate dose escalation and de-escalations. Once a maximum tolerated dose is identified and subjects from Part A have been followed for the 28-day DLT period, Part B of the study will commence. Part B of the	

Sponsor: Advaxis, Inc.	Name of Finished Product: ADXS11-001 MEDI4736	Type of Treatment: ADXS11-001: Lm -LLO Immunotherapy MEDI4736: MEDI4736 is a human monoclonal antibody (mAb) of the IgG1κ subclass that inhibits binding of programmed cell death-1 ligand (PD-L1) to programmed cell death-1 (PD-1) and CD8
		study will be a Phase 2 randomized design where subjects will be randomized 1:1:2 to ADXS11-001: MEDI4736: ADXS11-001+MEDI4736. Stratification will be based upon disease type. Safety will be assessed at every visit by comparing treatment-related adverse events (AEs), changes in physical examinations, vital signs measurements, and laboratory abnormalities.
Criteria for Evaluation		Safety: recorded AEs, changes in physical examinations, vital signs measurements and clinical laboratory evaluations Efficacy: Response rates as measured by RECIST 1.1 and irRECIST, duration of response, PFS

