4.2.4.2 Safety Endpoints

The primary safety objective of this trial is to characterize the safety and tolerability of ADXS11-001 alone, MEDI4736 alone, and ADXS11-001 in combination with MEDI4736 in subjects with previously treated locally advanced or metastatic SSCHN or cervical cancer. The primary safety analysis will be based on subjects who experience toxicities as defined by NCI CTCAE v 4.03. Safety will be assessed by quantifying the toxicities and grades, including SAEs and events of clinical interest (ECI) experienced by subjects who have

received ADXS11-001, MEDI4736, or ADXS11-001 + MEDI4736 combination therapy. The attribution to drug, time-of-onset, duration of the event, its resolution, and any concomitant medications administered will be recorded. AEs will be analyzed including but not limited to all AEs, SAEs, fatal AEs, and laboratory changes.

4.2.4.3 [REDACTED]

[REDACTED]

[REDACTED]

[REDACTED]

[REDACTED]

[REDACTED]

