5.2.2.2 ADXS11-001 Monotherapy (Part B)

In Part B, the dose for ADXS11-001 monotherapy will be 1×10^9 cfu administered in 250 mL of normal saline infused [REDACTED] Q4W (Weeks 1 and 5 in each 8-week cycle). Subjects should be premedicated with NSAIDS and oral antiemetics and received antibiotic as indicated in Section 7.1.4.2.

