5.2.2.3 MEDI4736 Monotherapy (Part B)

In Part B, the dose for MEDI4736 monotherapy will be 10 mg/kg administered in 250 mL of normal saline infused [REDACTED] in duration Q2W (Weeks 1, 3, 5, and 7 in each 8-week cycle).

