6.2 Trial Flow Chart for ADXS11-001 Monotherapy (Part B)

Trial Period:	Screening Phase		Treatment Period								Follow up		
Treatment Cycle/Title:	Pre-screening	Screening	Wk 1	Wk 2	Wk 3	Wk 4	Wk 5	Wk 6	Wk 7	Wk 8	Discon	Follow-up Phone Call ²	Follow Up
Scheduling Window (Days):		-28 to -1	$\pm 3^1$				± 3				At time of Discon	30/90 days post discon	Every 8 weeks post discon
Administrative Procedures													
Pre-screening Consent (H&N Subjects only)	X												
HPV+ Test (H&N subjects only)	X												
Informed Consent		X											
Inclusion/Exclusion Criteria		X											
Subject Identification Card		X											
Demographics and Medical History		X											
Prior and Concomitant Medication Review		X	X				X						
ADXS11-001 Administration (Q4wk) ³			X				X						
Clinical Procedures/Assessments													
Review Adverse Events			X				X				X	X	
Physical Examination ⁴		X	X				X				X		
Vital Signs and Weight ⁵		X	X				X				X		
ECOG Performance Status		X	X				X				X		
Tumor Imaging ⁶			X	X							X		X
Laboratory Assessments⁷													
Pregnancy Test – Urine or Serum β -HCG		X	X				X						
PT/INR and aPTT		X	X				X				X		
CBC with Differential		X	X				X				X		
Comprehensive Serum Chemistry Panel		X	X				X				X		
Urinalysis		X	X				X				X		

Trial Period:	Screening Phase		Treatment Period								Follow up		
	Pre-screening	Screening	Wk 1	Wk 2	Wk 3	Wk 4	Wk 5	Wk 6	Wk 7	Wk 8	Discon	Follow-up Phone Call ²	Follow Up
Treatment Cycle/Title:													
Scheduling Window (Days):		-28 to -1	$\pm 3^1$				± 3				At time of Discon	30/90 days post discon	Every 8 weeks post discon

Tissue/Blood Collection

1 - The +/- 3 day window does not apply to Cycle 1, Week 1. This window is only applicable in all subsequent cycles.

2 - Safety Follow up will be conducted via telephone. Safety Follow up at 30 days (± 1 week) for AEs and at 90 days (± 1 week) for SAEs.

3 - Subjects will receive prophylactic NSAIDS and antiemetics [REDACTED] before each ADXS11-001 infusion. Subjects will also receive a course of oral antibiotics to be started 3 days after each ADXS11-001 infusion

4 - ECG and O₂ saturation by pulse oximetry at baseline screening only

5 - Vital signs are to be monitored [REDACTED] following each ADXS11-001 infusion.

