7.1.2.3 Vital Signs

The investigator or qualified designee will take vital signs at screening, prior to the administration of each dose of trial treatment, [REDACTED] following each ADXS11-001 infusion and at treatment discontinuation as specified in the Trial Flow Chart (Section 6.0). Vital signs should include temperature, pulse, respiratory rate, and blood pressure. Height will be measured at screening only and weight will be measured pre-dose at each visit.

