8.0 STATISTICAL ANALYSIS PLAN

8.1 Statistical Analysis Plan Summary

This is a Phase 1-2 study of ADXS11-001 or MEDI4736 alone or combination in locally advanced, or metastatic, squamous or non-squamous carcinoma of the cervix or HPV+ squamous cell carcinoma of the head and neck.

There are 2 phases in this study with different objectives. For safety, the analysis will be performed for Part A and Part B separately and combined. The efficacy analysis will be performed for Part A and Part B separately. SAS 9.2 or higher will be used for data analysis.

Subject disposition, demographic and baseline subject characteristics will be summarized separately for Part A and Part B. Adverse events will be classified and summarized by type, incidence, severity, and causality. All adverse events will be summarized by subject, treatment, and disease. All subjects who receive at least 1 dose of study treatment will be included in the safety analyses.

Statistical analysis for efficacy will be summarized by treatment arm and disease type. Although it may lack statistical power, statistical testing for treatment comparisons will be performed as a reference. Tumor response will be evaluated by RECIST criteria and secondarily by irRECIST criteria. The overall response rate will be summarized; frequency counts and percentage and will be tested by the Fisher's Exact test. PFS is defined as the time from randomization until objective tumor progression or death. Subjects who have not progressed or who are still alive at the time of evaluation will be censored for the analysis. Kaplan-Meier (KM) curves and descriptive statistics will be used to summarize PFS. The percentage of subjects with PFS and the 95% confidence intervals will be provided. PFS and duration of response will be summarized using KM method and tested by the Log-Rank test controlled by disease type.

Furthermore, the disease response will be tabulated for all subjects who receive ADXS11-001 monotherapy, MEDI4736 monotherapy or ADXS11-001 + MEDI4736 combination therapy.

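### Part B safety assessments are scheduled half as often with ADXS11-001 alone as in the two MEDI4736 arms, so by-arm summaries of silent, short-lived laboratory, examination and vital-sign findings tend to favour ADXS11-001 alone.

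*Combined protocol and SAP*

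**What the plan says.** The methodology paragraph of Section 1.0 describes the safety assessment: "Safety will be assessed at every visit by comparing treatment-related adverse events (AEs), changes in physical examinations, vital signs measurements, and laboratory abnormalities". Section 4.2.4.2 gives the primary safety objective as to "characterize the safety and tolerability of ADXS11-001 alone, MEDI4736 alone, and ADXS11-001 in combination with MEDI4736". Section 8.1 adds: "All adverse events will be summarized by subject, treatment, and disease".

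Dosing differs by arm. ADXS11-001 alone is given at "Weeks 1 and 5 in each 8-week cycle" (Section 5.2.2.2). MEDI4736 alone is given at "Weeks 1, 3, 5, and 7 in each 8-week cycle" (Section 5.2.2.3). The combination also has visits at Weeks 1, 3, 5 and 7 (Section 5.2.2.1).

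Assessments follow dosing. Chart 6.2 places on-treatment adverse-event review, physical examination, vital signs, ECOG status, blood count, chemistry, coagulation and urinalysis at Weeks 1 and 5. Charts 6.3 and 6.4 place them at all four visits. Sections 7.1.2.2 to 7.1.2.4 and 7.1.4.2 likewise tie examination, vital signs, ECOG status and laboratory tests to each dose. Vital signs after infusion are required only "following each ADXS11-001 infusion and at treatment discontinuation" (Section 7.1.2.3), so none are scheduled after MEDI4736 given alone.

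Charts 6.1, 6.3, 6.4 and 6.5 have a T3, T4 and TSH row. Chart 6.2 as it reads here does not.

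**The concern.** A worst-grade or any-occurrence table counts what was found, and what is found depends on how often one looks. If two arms had identical true rates of a silent, transient laboratory abnormality, the arm with four-weekly draws would show fewer.

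Safety of the combination is a Part B primary objective (Section 3.4), and the single-agent arms are the natural reference for what the combination adds. Part of an apparent excess over ADXS11-001 alone could therefore be an effect of the schedule. Section 8.1 does not set common time points, allow for the number of assessments, or mention the imbalance. It also asks for safety to be summarised with Parts A and B combined. All Part A subjects are on the two-weekly combination schedule, so pooling enlarges only the more intensively assessed side.

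Post-infusion vital signs raise a similar problem in the other direction: MEDI4736 alone has no scheduled readings to set against those of the two arms that receive ADXS11-001.

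**Working it through.** The documents give no figure for this point, so there is nothing to reproduce. The visit counts come from the documents; the durations below are assumptions.

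**Scheduled visits.** Per 8-week cycle: 2 (Weeks 1, 5) against 4 (Weeks 1, 3, 5, 7). Over the maximum of 52 weeks: 52/4 = 13 against 52/2 = 26. The ratio is 0.50 over any whole number of cycles, so early discontinuation does not change it.

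**Detection model.** Take one abnormality that can be found only if present at a scheduled visit, with onset uniform between visits. Ignore visit windows and unscheduled assessments. T is the visit interval, 14 or 28 days.

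*Fixed duration d:* P = min(1, d/T). Four-weekly against two-weekly detection is 25% against 50% at 7 days, 50% against 100% at 14 days, 75% against 100% at 21 days, and 100% in both from 28 days.

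*Exponential duration with mean m:* P = (m/T)(1 − exp(−T/m)). The ratio of four-weekly to two-weekly detection simplifies to (1 + exp(−14/m))/2, so the share missed is (1 − exp(−14/m))/2. For m = 14 this is (1 − 0.368)/2 = 0.316.

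| Assumed mean m (days) | Two-weekly | Four-weekly | Share missed |
|---|---|---|---|
| 7 | 43% | 25% | 43% |
| 14 | 63% | 43% | 32% |
| 21 | 73% | 55% | 24% |
| 30 | 80% | 65% | 19% |
| 63 | 90% | 81% | 10% |
| 90 | 93% | 86% | 7% |

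The direction is the same throughout. The size depends on duration.

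**Thyroid testing, passages side by side.** Chart 6.2 shows no thyroid row. Table 9 (Section 7.1.2.14.1) lists T3, T4 and TSH under its other tests without restricting them by arm. Sections 7.1.4.1 and 7.1.4.2 call for that category at screening and before dosing. Chart 6.5 has the thyroid row and serves subjects retreated with their assigned treatment (Section 7.1.4.2.1), which includes ADXS11-001 alone. Section 7.2.3.2 makes Grade 3 or higher thyroid events reportable in every arm. These passages do not agree.

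**The case against.** Four objections have force.

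- **Adverse events are not snapshots.** Section 7.2 has them recorded from consent to 30 days after treatment in every arm, and Section 7.1.2.1 allows extra assessment when clinically indicated. A visit review can also capture a symptom that has already resolved. A reader might infer from the visit ratio that adverse-event counts in the ADXS11-001 arm will be roughly halved. The documents do not support that. The detection model does not apply to symptomatic events, and no bias in them has been quantified.
- **Thyroid.** A reader might infer from chart 6.2 that every asymptomatic thyroid abnormality in this arm will be missed. Table 9, Sections 7.1.4.1 and 7.1.4.2, and chart 6.5 prevent that conclusion. Chart 6.2 also breaks across a page just after urinalysis, so a row lost in reading the PDF cannot be excluded. What stands is a conflict to be reconciled.
- **Size.** The larger losses need short durations, which the documents do not give. The typical ADXS11-001 reactions start within hours and resolve quickly (Sections 4.2.3.1 and 5.6.1), so pre-dose visits on either schedule would seldom catch them. Both ADXS11-001 arms have post-infusion vital signs.
- **Status of the comparison.** The Section 1.0 sentence does not say that the comparing is between arms. Safety is summarised descriptively, and the testing of treatment comparisons belongs to efficacy. With 48 subjects at 1:1:2, or 12:12:24, one subject in a single-agent arm is 1/12, about 8 percentage points.

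These limit the point to silent, transient findings and to interpretation. They do not remove it, because Sections 4.2.4.2 and 8.1 still set the arms side by side.

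**Conclusion.** The point holds in limited form. Scheduled on-treatment looks are exactly half as frequent with ADXS11-001 alone, and nothing in the plan allows for it. By-arm summaries of laboratory, examination and pre-dose vital-sign abnormalities will tend to favour that arm for silent findings that resolve between visits. Under exponential durations with means of 7 to 30 days, 43% down to 19% of what two-weekly assessment would detect is missed. The loss is 10% at a mean of about 63 days, and nil for fixed durations of 28 days or more. All of this rests on assumed durations and uniform onset.

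The effect on symptomatic, serious or persistent adverse events is expected to be small. Because the safety summaries are descriptive, this is a bias in interpretation; no error rate is at stake. It is worth correcting because the remedy is cheap.

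**What to change.** In Section 8.1:

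1. Keep the all-values tables. Beside them, add between-arm worst-grade, shift and Grade 3 or higher tables for laboratory, examination and pre-dose vital-sign findings, limited to assessments scheduled in all arms: baseline, pre-dose Weeks 1 and 5 of each cycle, and discontinuation. Base between-arm statements about these findings on the added tables.
2. Compare post-infusion vital signs only between ADXS11-001 alone and the combination.
3. State the unequal visit frequency beside the adverse-event table by arm, and repeat that table for Grade 3 or higher adverse events and for serious adverse events.
4. Reconcile chart 6.2 with Table 9, Sections 7.1.4.1 and 7.1.4.2, and chart 6.5 on thyroid testing. Contrast thyroid results only between arms in which the panel was actually scheduled and collected.

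The cost is SAP wording, a few extra tables and one document reconciliation. The analysis changes add no visit, sample or subject. The common-visit tables use fewer values from the MEDI4736 arms, which is why they should accompany the full tables and not replace them. They also cannot undo treatment holds triggered by Week 3 or Week 7 findings under Table 4, since later Week 1 and Week 5 values already reflect those holds.

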2.0 TRIAL DESIGN

Specific procedure to be performed during this trial, as well as the prescribed times and associated visit window are outlined in the Study Flow Charts - Section 6.0. Details of each procedure are provided in Section 7.1 - Trial Procedures.

This is a multi-center, open-label, 2 part randomized study of ADXS11-001 and MEDI4736 administered as monotherapy or in combination to subjects with metastatic squamous or non-squamous carcinoma of the cervix or metastatic HPV+ squamous cell carcinoma of the head and neck (SCCHN).

2.1 ADXS11-001 + MEDI4736 Combination Therapy

Part A of the study will be Phase 1 analysis of ADXS11-001 given in combination with MEDI4736. A standard 3+3 study design will guide enrollment, dose escalations, and de-escalations during Part A. The dose limiting toxicity (DLT) evaluation period will be 28 days. The dose of ADXS11-001 will be held at 1×10^9 cfu; escalating doses of MEDI4736 (3 mg/kg and 10 mg/kg) will be evaluated as Dose Level 1 and Dose Level 2, respectively. Dose Level -1 will be ADXS11-001 (1×10^9 cfu) and MEDI4736 (1 mg/kg), and will be explored if Dose Level 1 is not tolerated, as dictated by the 3+3 design. ADXS11-001 will be dosed every 4 weeks. MEDI4736 will be dosed every 2 weeks. Subjects will continue on therapy for up to 1 year or until they discontinue due to documented progression, unacceptable toxicity, Investigator's decision to withdraw the subject, subject withdraws consent, pregnancy of the subject, noncompliance with trial treatments or procedure requirements, administrative reasons, or withdrawal from the study. The primary objective of Part A is to determine the safety and tolerability of the treatment combination. Secondary endpoints will include evaluation of response rates, duration of response and progression free survival (PFS) as determined by Response Evaluation Criteria in Solid Tumors (RECIST 1.1) and secondarily by irRECIST. Response and progression will be determined by the investigator.

2.2 ADXS11-001 vs MEDI4736 vs ADXS11-001 +MEDI4736

Part B of the study will start once subjects from Part A have been followed through the 28-day DLT period. Part B will be a Phase 2 design which will randomize subjects 1:1:2 to ADXS11-001 : MEDI4736 : ADXS11-001+MEDI4736. Randomization will be stratified based upon disease type. ADX11-001 will be administered every 4 weeks. MEDI4736 will be administered every 2 weeks. [REDACTED]

[REDACTED] Subjects will continue on therapy for up to 1 year or until they discontinue due to documented progression, unacceptable toxicity, investigator's decision to withdraw the subject, subject withdraws consent, pregnancy of the subject, noncompliance with trial treatments or procedure requirements, administrative reasons, or withdrawal from the study. Subjects who achieve a complete response (CR) should receive at least 1 additional cycle of treatment. Crossover to another treatment arm will not be allowed. Adverse events will be monitored throughout the study and graded in severity according to the guidelines outlined in the National Cancer Institute (NCI) Common Terminology Criteria for Adverse Events (CTCAE) version 4.03.

After the end of treatment, each subject, regardless of whether they participate in Part A or Part B, will be followed for a minimum of 30 days for adverse event monitoring (serious adverse events will be collected for up to 90 days) after the end of treatment. Subjects will have post treatment follow up visits for disease status, including non-study cancer treatment and disease progression, for up to 3 years.

Safety and efficacy analysis will be performed for both parts of the study. Subject disposition, demographic and baseline characteristics will be summarized separately for Part A and Part B. Adverse events will be classified and summarized by system organ class (SOC) and preferred term, incidence, severity, and causality. All subjects who receive at least 1 dose of study drug will be included in the safety analyses.

[figure not shown]
Statistical analysis for efficacy will be performed by treatment arm and disease type. Although it may lack statistical power, statistical testing for treatment comparisons will be

performed as a reference. Tumor response will be evaluated by RECIST 1.1 criteria and secondarily by irRECIST criteria. The overall response rate will be summarized by frequency counts and percentage, and will be tested by Fisher's Exact test. PFS is defined as the time from randomization until objective tumor progression or death. Subjects who have not progressed or died will be censored for the analysis. Kaplan-Meier (KM) curves and descriptive statistics will be used to summarize PFS. The percentage of subjects with PFS and the 95% confidence intervals will be provided. PFS and duration of response will be summarized using KM method and tested by the Log-Rank test controlled by disease type.

Furthermore, disease response will be tabulated for all subjects who receive ADXS11-001 monotherapy, MEDI4736 monotherapy, or ADXS11-001 + MEDI4736 combination therapy.

2.3 Trial Diagram

ADXS11-001 + MEDI4736 in Metastatic Cervical Cancer or HPV+ SCCHN

3.0 OBJECTIVES & HYPOTHESES

3.1 Part A - Primary Objectives & Hypothesis

Objective: To evaluate the safety and tolerability of ADXS11-001 administered in combination with MEDI4736 across 2 dose levels by NCI CTCAE v 4.03.

Objective: To select recommended dose for Part B of the study based on number of DLTs seen in subjects enrolled in Part A.

Hypothesis: ADXS11-001 administered in combination with MEDI4736 will be well tolerated at the maximum doses combined.

